11. SAFETY

Safety endpoints will be analyzed using the Safety population. Safety endpoints will be summarized descriptively as described in section 3.1.

11.1 Adverse Events

AEs and serious AEs (SAEs) are defined in the study protocol.

Treatment Emergent Adverse Events (TEAEs) are defined as adverse events that occurred following the first administration of study medication. If missing dates or time prevent a clear determination as to whether the AE is treatment emergent, the adverse event will be regarded TEAE.

All AE verbatim terms will be coded using the most recent version of MedDRA. All AE summaries will be restricted to include TEAEs only. AEs occurring prior to first dose of study medication will be listed but not included in any tabulations. Summary tables will include the number of participants (%) experiencing an event and the number of events. Participants will be counted only once for each SOC and PT level (categorical descriptive analysis).

The TEAE summaries will include:

- Overall summary of TEAEs.
- Summary of TEAEs by SOC, PT and Relationship.
- Summary of TEAEs by SOC, PT and Severity.
- Summary of Definitely Related TEAEs by SOC, PT and Severity
- Summary of Probably or Possibly Related TEAEs by SOC, PT and Severity
- Summary of TEAEs of Special Interest by SOC, PT and Severity
- Summary of serious TEAEs by SOC and PT.
- Summary of Treatment Related serious TEAEs by SOC and PT
- TEAE summary of events leading to the study drug withdrawal by SOC and PT.
- Treatment Related TEAE summary of events leading to the study drug withdrawal by SOC and PT

For the 'Overall Summary of TEAEs', the following items will be included:

1. Any TEAEs
2. Any serious TEAEs
3. Any TEAEs leading to study discontinuation
4. Any TEAEs of special interest
5. Any related TEAE
6. Any TEAEs leading to study discontinuation
7. Any TEAEs leading to death

All AEs will be listed and will include the start and stop date and time of AEs, AE number, verbatim term, Preferred Term, System Organ Class, SAE/TEAE flag, actions taken for AE, relationship to study treatment and outcome.

Separate by-participant data listings will be created for SAEs, AEs leading to study discontinuation, and AEs leading to death. These listings will be presented by participant ID and AE start date/time for the Safety Population.

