14.2. Adverse and Serious Adverse Events

In this study, AEs will be reported for all subjects from the time of consent until the completion of the EOS/ET visit. SAEs will be reported for all subjects (enrolled and not enrolled) from the time of consent. Adverse events reported from the time of consent to pre-dose on Day 1 will be recorded as pre-treatment AEs. Treatment emergent- AEs will be evaluated from the first administration of IP until the EOS/ET visit. Adverse events that are deemed related to treatment and are ongoing 14 days post EOS/ET visit for non-serious AEs and 60 days post EOS/ET visit for serious AEs, the AE outcome will be recorded (e.g. Not Recovered or Recovering) depending on the status and entered on the AE eCRF page (see [Section 14.2.1.4](#)).

All spontaneously volunteered and enquired for, as well as observed AEs, will be recorded in the subject's medical records and the eCRF.

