2.3.2 Secondary endpoints(s)

Stage 1:

- Reduction of subcutaneous fat thickness as measured by ultrasound compared with Baseline. [Time frame: Day 1 and Week 4]
- Reduction of subcutaneous fat volume over the treated area as measured by ultrasound compared with Baseline. [Time frame: Day 1 and Week 4]

*Note: no efficacy endpoints/objectives will be assessed for Group 1 of Stage 1 study.

Stage 2:

- Reduction of subcutaneous fat volume over the treated area as measured by ultrasound from Baseline to follow-up visits compared with placebo. [Time frame: Visit 2 (Baseline), Visit 6, and Visit 7]
- Reduction of subcutaneous fat volume over the treated area of the CBL-514 group as measured by ultrasound compared with individual Baseline. [Time frame: Visit 2 (Baseline), Visit 3, Visit 4, Visit 5, Visit 6, and Visit 7]
- Number of treatments required to first occurrence of reducing at least 150 mL of subcutaneous fat volume over the treated area as measured by ultrasound in CBL-514 group. [Time frame: from Visit 2 (Baseline) to Visit 7]
- The proportion of subjects who lose at least 200 mL of subcutaneous fat as measured by ultrasound from baseline to follow-up visits compared with placebo. [Time frame: Visit 2 (Baseline), Visit 6, and Visit 7]
- Safety as assessed by recording of TEAEs, laboratory assessments, vital signs, ECGs, physical examinations, and ISRs compared with placebo

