2.5 Randomization

Stage 1 of the study will be open label with a total of 24 subjects sequentially enrolled in 4 dose groups (6 subjects in each group) to receive one course of allocated CBL-514 dose as presented in Table 1. Once deemed eligible for enrolment in the study, each subject will be assigned a sequential subject number prior to first dosing.

Stage 2 of the study will be a randomized, single-blind, parallel-group. Considering drop-out rates (16% CBL-514 group vs 44% placebo group), approximately 75 subjects are planned to be enrolled and randomized 2:1 (50 subjects in the CBL-514 group and 25 subjects in the placebo group) in order to have a total of at least 56 evaluable subjects in Stage 2 of the study. The dose of CBL-514 used in Stage 2 will be set no higher than the highest safe dose from Stage 1. Once deemed eligible for enrolment in the study, each subject will be assigned a sequential randomization number prior to first dosing.

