8. TREATMENT EXPOSURE

Treatment exposure (total number of injections, total volume administrated, total Dose administrated) will be summarized using descriptive statistics in accordance with section 3.1 based on the Safety population. All study drug administration information (study drug administered (Yes/No), reason not administered, start and end date and time of administration, Lignocaine application, total volume administrated, total number of injections, study drug given per protocol (Yes; details of administration/No; Reason not given per protocol) will be presented in the by-participant data listings.

Total administrated dose can be calculated as below:

$$\text{Total Dose Administrated (mg)} = \text{Total Volume Administered (mL)} \times 5 \text{ mg/mL}$$

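### Stage 2 adverse events are compared with placebo by crude percentages and raw counts only, with no allowance for unequal time at risk or number of courses

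*SAP*

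**What the plan says.** The Stage 2 secondary endpoints in SAP 2.3.2 (and Protocol 7.2.2.2) include safety, ending with "physical examinations, and ISRs compared with placebo". The comparison with placebo is therefore part of the endpoint.

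For adverse events, SAP 11.1 states: "Summary tables will include the number of participants (%) experiencing an event and the number of events". Under SAP 3.1 the percentages are taken over participants in the analysis population. Under SAP 4.1.3 the Safety population holds everyone randomized and dosed at least once, so a subject who leaves after one course counts as much as one followed to the end. Neither document plans a rate per unit of time, a rate per course or a time-to-first-event summary.

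On the observation window, Protocol 14.2 states: "Treatment emergent- AEs will be evaluated from the first administration of IP until the EOS/ET visit". Protocol 12.2.6 makes the ET visit the end of participation for those who withdraw.

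On expected losses, SAP 2.5 states: "Considering drop-out rates (16% CBL-514 group vs 44% placebo group), approximately 75 subjects are planned to be enrolled and randomized 2:1". On courses, SAP 2.1 allows up to four, and a subject without enough residual fat stops treatment early, goes on to Visits 6 and 7, and is not counted as discontinued.

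SAP 8 does plan an exposure summary: "Treatment exposure (total number of injections, total volume administrated, total Dose administrated) will be summarized using descriptive statistics". It stands apart from the adverse event tables and does not list weeks at risk.

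**The concern.** A crude percentage compares two arms fairly only if both are observed for about the same time and injected about the same number of times. The plan's own drop-out figures differ by a factor of 2.75 (44/16), and courses can also be cut short for a reason that depends on whether the drug works. Raw event counts are not comparable in any case, because allocation is 2:1.

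At stake is how the safety comparison is read. Some of an apparent difference, or of an apparent absence of difference, could come from exposure, and the planned adverse event tables give no means of judging how much.

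**Working it through.** **Inputs.** Drop-out d = 0.16 and 0.44 (SAP 2.5). Arms: "50 subjects in the CBL-514 group and 25 subjects in the placebo group". Participation about 20 weeks (Protocol synopsis, Duration of Treatment). Courses at weeks 0, 4, 8 and 12 (Protocol Table 5). The timing of drop-out is not given, so a range is assumed. The first calculations treat d as true loss to follow-up.

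**The plan's own figure.** 50 × (1 − 0.16) = 42 and 25 × (1 − 0.44) = 14, total 56. This matches the evaluable target.

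**Time at risk and courses per subject.** Weeks = (1 − d) × 20 + d × t, where t is the mean drop-out week. Courses = (1 − d) × 4 + d × c, where c is the mean number of courses among drop-outs. For drop-out uniform over 20 weeks, t = 10 and c = (1 + 2 + 3 + 4 + 4)/5 = 2.8. This gives 0.84 × 20 + 0.16 × 10 = 18.40 weeks against 0.56 × 20 + 0.44 × 10 = 15.60, and 0.84 × 4 + 0.16 × 2.8 = 3.81 courses against 0.56 × 4 + 0.44 × 2.8 = 3.47.

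| Assumed drop-out timing | t, c | Weeks, CBL-514 vs placebo | Ratio | Courses, CBL-514 vs placebo | Ratio |
|---|---|---|---|---|---|
| Uniform, weeks 0–20 | 10, 2.8 | 18.40 vs 15.60 | 1.18 | 3.81 vs 3.47 | 1.10 |
| Uniform, weeks 0–12 | 6, 2 | 17.76 vs 13.84 | 1.28 | 3.68 vs 3.12 | 1.18 |
| All at week 4, before course 2 | 4, 1 | 17.44 vs 12.96 | 1.35 | 3.52 vs 2.68 | 1.31 |
| All at week 16 | 16, 4 | 19.36 vs 18.24 | 1.06 | 4.00 vs 4.00 | 1.00 |

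With no drug effect, the expected ratio of events per subject equals the exposure ratio that drives the event.

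**Crude percentages.** Assume the same constant hazard in both arms and a 20-week risk of 30%. The expected crude percentage is (1 − d) × 0.30 + d × F, where F is a drop-out's risk up to leaving. F is 0.159 (uniform over 20 weeks), 0.069 (week 4) or 0.248 (week 16).

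- Uniform: 27.7% vs 23.8%.
- Week 4: 26.3% vs 19.8%.
- Week 16: 29.2% vs 27.7%.

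Drop-out alone thus yields a spurious excess on CBL-514 of about 4, 6.5 and 1.5 points. If risk attaches to courses instead, the excess for risks of 10% to 60% is 0.8 to 4.1 points (uniform), 2.1 to 11.1 points (week 4) and zero (week 16).

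**The opposing force.** Suppose a share s of CBL-514 completers stop after two courses for insufficient fat and finish about week 12 (week 4 plus 8 weeks), with no such stopping on placebo. Under uniform drop-out, weeks = 18.40 − 0.84 × s × 8 and courses = 3.81 − 0.84 × s × 2.

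- s = 20%: 17.06 weeks and 3.47 courses; ratios 1.09 and 1.00.
- s = 50%: 15.04 weeks and 2.97 courses; ratios 0.96 and 0.855.

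The net direction depends on s, which the documents do not give.

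**The case against.** The strongest reply has four parts.

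*The drop-out figures may not be lost time.* They serve to get from randomized to evaluable subjects: "in order to have a total of at least 56 evaluable subjects in Stage 2 of the study". The sample-size text does not define evaluable. If part of the 44% reflects exclusions such as visits outside a window, those subjects may have been fully followed for adverse events, and the gap shrinks. This stands as a limit on size. However, the documents do call the figures drop-out, and Protocol 9.6 requires removal from the study for several Stage 2 reasons, including weight change and a long treatment interval.

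*The commonest events are little affected.* Protocol 6.2.2 reports that injection site reactions were the most frequent events in the earlier study. Every subject in the Safety population has at least one course, so the crude percentage for a reaction seen in most subjects after the first course barely moves. This stands for percentages. It does not protect event counts or events that accrue later.

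*Safety is descriptive and exposure is reported.* Protocol 16 plans no formal testing, SAP 8 tabulates injections, volume and dose, and SAP 5.1.1 reports withdrawals with reasons. A careful reader would see some of the imbalance, and no test is invalidated. But a descriptive comparison still needs comparable denominators, and weeks at risk and courses are not tabulated.

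*The shifts are small beside sampling error.* Near 25%, the standard error of a difference is √(0.25 × 0.75 × (1/50 + 1/25)) = 10.6 points, so shifts of about 4 and 6.5 points are roughly 0.4 and 0.6 standard errors. This stands, and it limits the weight of the point. It does not remove a systematic shift that the tables would leave invisible.

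Replacing drop-outs (Protocol 9.5) does not help, because dosed drop-outs stay in the Safety population.

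**Conclusion.** The gap is real but modest: an interpretability weakness in a descriptive secondary comparison, and a cheap improvement. If the 16% and 44% are true losses over about 20 weeks, the CBL-514/placebo ratio from drop-out alone is 1.06 to 1.35 for time at risk and 1.00 to 1.31 for courses. The range reflects the unstated timing.

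A reader might infer that CBL-514 is bound to look worse than placebo, or that the safety comparison is invalid. The documents support neither. Stopping for insufficient fat can cancel or reverse the imbalance, drop-out after the fourth course leaves the number of courses equal, and part of the planned loss may be non-evaluability. What can be said is that the crude contrast could overstate or understate harm and that the planned adverse event tables would not show which.

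**What to change.** In SAP 11.1, keep the crude tables. To the Stage 2 TEAE, related-TEAE and AESI summaries (Stage 2 tables in the 14.3.3 series), add by arm:

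- subject-weeks at risk, from first dose to EOS/ET, with the recorded withdrawal date used where no ET visit took place;
- number of courses given;
- event rates per subject-week and per course;
- optionally, incidence after course 1 (before course 2) as a like-for-like comparison.

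Any between-arm rate ratio or difference should be optional, descriptive and limited to any TEAE, any related TEAE and any AESI. Its interval must allow for repeated events within a subject, for example through a robust variance or a subject-level bootstrap. Where placebo has no events, show the rates without a ratio.

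The cost is SAP wording and a few columns. Administration dates (Protocol 10.6), withdrawal dates (Protocol 9.6) and event dates (SAP 11.1) are already collected. The rates assume roughly constant risk, they do not correct for drop-out related to outcome, and a course may be 25 to 50 injections, so a per-course rate does not fully equalize exposure. The injection totals in SAP 8 should be read beside it.

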11.2 Safety Laboratory Assessments

Blood and urine samples will be collected at the time points specified in the Schedule of Events (refer to the Protocol) to conduct hematology, chemistry and urinalysis (including microscopic examinations) analyses.

The following tests will be performed within each of the specified test panels:

Hematology:

1. Hemoglobin (Hb)
2. Hematocrit (Hct)
3. Erythrocytes (RBC)
4. Platelets (PLAT)
5. Leukocytes (white blood cells [WBCs]) with differential (including Eosinophils [ESN], Neutrophils [NEUT], Basophils [BASO], Lymphocytes [LYM], and Monocytes [MONO])
6. Mean corpuscular volume.

Biochemistry:

1. Urea (U)
2. Creatinine (CREAT)
3. TBIL
4. Albumin (ALB)
5. ALKP (ALP)
6. AST
7. ALT
8. GGT
9. Estimated Glomerular Filtration Rate (eGFR)
10. Glycated hemoglobin (HbA1c)
11. Fasting Blood Sugar (FBS)
12. Sodium (NA)
13. Potassium (K)
14. Chloride (CL)
15. Bicarbonate (BICARB)
16. Triglyceride
17. Total cholesterol

18. LDL-C

19. HDL-C

Coagulation:

20. International Normalized Ratio (INR)

21. Activated Partial Thromboplastin Time (aPTT)

22. Prothrombin Time.

Urinalysis & Microscopic Urinalysis:

A urinalysis test (dipstick) will be performed for each subject. If clinically significant abnormality is noted for protein, blood, or leukocyte esterase (and at the discretion of the Investigator) a microscopic examination of RBC, WBC, bacteria, and casts will be performed.

All laboratory data collected at scheduled and unscheduled visits will be included in the listings, but only results collected as scheduled visits will be included in the summary tables.

Results for individual parameters may be reported in different units depending on the analyzing laboratory. If required, the results (and the corresponding normal range cut-off values) for individual parameters may be converted to International System of Units (S.I.) units to summarize the data.

For all the parameters where a unit value has been reported, the parameter names that will be used in the outputs will comprise of the test name and the unit of measure, for example, 'Albumin (g/L)'. For the urinalysis parameters, the parameter name will be the reported test name only. Parameters will be sorted alphabetically within tables and listings.

For all parameters where a normal range limit value was reported, the normal range will be derived based on the available lower and upper limit values and any reported mathematical symbols. If both a lower and upper limit value is available, the normal range will be presented as '(Lower, Upper)'.

The reported results for each parameter with a defined normal range will be classified ('Low', 'Normal', 'High') in relation to the defined normal range limits. If a result is equal to the normal range cut-off value, the result will be considered 'Normal'.

The hematology and chemistry results tables will present summary statistics for each laboratory parameter within the specific test panel. For each parameter, summaries will be presented for the baseline and each scheduled post-baseline visit. In addition, summaries will be presented for the change from baseline values at each scheduled post-baseline visit (continuous descriptive analysis).

The change from baseline values at each post-baseline visit will be calculated for all parameters with continuous results (except for pH and Specific Gravity). The abnormal urinalysis result (dipstick and microscopy), if applicable, will be listed only.

The decimal precision to which the summaries for each parameter will be based on the maximum number of decimals to which the reported result or the normal range limits are presented to in the raw data. The results and normal ranges will be displayed to the same decimal precision in the listings.

Additionally, counts (%) of number participants with values out of normal range at each scheduled time point will also be presented along with shift tables that will represent the changes in normal range categories across post-baseline time points (categorical descriptive analysis).

The urinalysis table will present counts and percentages of normal, abnormal clinically significant and clinically significant for the reported results at baseline and each post-baseline visit for all parameters (categorical descriptive analysis).

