11. Subject is undergoing chronic steroid or immunosuppressive therapy, with the exception of oral steroid inhalation indicated for asthma management or topical steroid application for skin conditions that are not directly applied or indirectly affect the treatment area.
12. Requiring continual use of the following therapeutic agents during the study: terfenadine (Teldane), buspirone (Buspar), fexofenadine (Fexotabs, Tefodine, Telfast, Xergic, Allegra, etc.), any medication that is known to strongly inhibit or induce CYP enzymes (please refer to Section 24.1), sensitive CYP substrates or drugs with narrow therapeutic index, in the opinion of the investigator, may affect the evaluation of the study product or place the participant at undue risk.

If a subject needs to use the above mentioned therapeutic agents during the study for any reason, these therapeutic agents should not be used at least for 2 days prior to dosing and until 1 day post-dose.
13. Unable to receive local anesthesia (e.g., history of hypersensitivity to lidocaine).
14. Subjects with known allergies or sensitivities to the IP or its components.
15. Subjects with liver cirrhosis, with inadequate liver function at Screening defined as aspartate aminotransferase (AST), alanine aminotransferase (ALT), alkaline phosphatase (ALKP), total

bilirubin (TBIL), or gamma-glutamyl transferase (GGT) > 3.0 × upper limit of normal (ULN), or with any hepatic medical condition that would interfere with assessment of safety or efficacy or compromise the subject's ability to undergo study procedures or provide informed consent.

- Subjects with any renal impairment, defined as abnormal serum creatinine, and urea > 1.5 × ULN or estimated glomerular filtration rate (eGFR) < 90 mL/min/1.73 m². Subjects who are currently on dialysis should be excluded.

Subjects with an eGFR ≥ 60 and < 90 mL/min/1.73 m² at Screening should be evaluated by the Investigator to exclude pre-existing renal disease or associated dysfunction. If mild decrease in eGFR is assessed by the Investigator as not clinically significant or not related to dysfunction, the subjects may be eligible upon the Investigator's assessment.

- Use of other investigational drug or device within 12 weeks prior to Screening.

Withdrawal criteria

A subject must be removed from the study at any time, if any of the following criteria is met:

Stage 1

- Subject withdraws consent.

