8.4. Stopping Criteria

Administration of IP in a dose group may be paused, and additional subjects will not receive further treatments, until a consultation has taken place between the Investigator, the MM, and the Sponsor representative under the following circumstances:

- Any subject experiences an adverse event as Grade 3 (as defined in the NCI-CTCAE version 5.0) for cardiovascular, renal or hepatic event considered to be at least possibly related to IP,
- Except for cardiovascular, renal, or hepatic events specified in Criterion #1, any participant experiences an AE as Grade 4 and considered to be at least possibly related to IP
- Any subject experiences an SAE that is considered to be at least possibly related to the IP
- An AE or group of AEs that singularly or in aggregate suggests to the Investigator or Sponsor that the IP is poorly tolerated and further treatment PP may not be safe.

If any of these criteria occur, consultation between the Sponsor representative, the Investigator, and the MM will take place as soon as possible to evaluate the event. Subjects should remain in the study and be followed until the adverse event resolves or stabilizes.

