 - f. Evidence of any cause of enlargement in the area to be treated other than localized abdominal or thigh subcutaneous fat,
 - g. Tattoos on the area to be treated.
9. Subject who has undergone the following procedures:
 - a. Previous surgery which caused scar tissues on the anticipated treatment area before Screening or during the study, except laparoscopic surgery and surgery which causes very small scar tissues would be eligible as per Investigator's discretion,
 - b. Liposuction to the region to be treated before Screening or during the study,
 - c. Esthetic procedure e.g. cryolipolysis, ultrasonic lipolysis, LLLT, lipolysis injection to the region to be treated within 12 months before Screening or during the study.
 - d. Using medication which is delivered via subcutaneous injection at the treatment area during the study period.
10. Subject is on prescription or OTC weight reduction medication or weight reduction programs within 3 months before Screening or during the study.

11. Subject is undergoing chronic steroid or immunosuppressive therapy, with the exception of oral steroid inhalation indicated for asthma management or topical steroid application for skin conditions that are not directly applied or indirectly affect the treatment area.
12. Requiring continual use of the following therapeutic agents during the study: terfenadine (Teldane), buspirone (Buspar), fexofenadine (Fexotabs, Tefodine, Telfast, Xergic, Allegra, etc.), any medication that is known to strongly inhibit or induce CYP enzymes (please refer to Section 24.1), sensitive CYP substrates or drugs with narrow therapeutic index, in the opinion of the investigator, may affect the evaluation of the study product or place the participant at undue risk.
If a subject needs to use the above mentioned therapeutic agents during the study for any reason, these therapeutic agents should not be used at least for 2 days prior to dosing and until 1 day post-dose.
13. Unable to receive local anesthesia (e.g., history of hypersensitivity to lidocaine).
14. Subjects with known allergies or sensitivities to the study treatment or its components.
15. Subjects with liver cirrhosis, with inadequate liver function at Screening defined as AST, ALT, ALKP, TBIL, or GGT $> 3.0 \times \text{ULN}$, or with any hepatic medical condition that would interfere with assessment of safety or efficacy or compromise the subject's ability to undergo study procedures or provide informed consent.

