14.2.4. Notification of a Serious Adverse Event

In order to meet the requirements for expedited reporting of SAEs meeting specific requirements to applicable regulatory authorities and institutional ethics committees, all SAEs, **must be reported to Sponsor or Sponsor’s representative within 24 hours** from the time the site investigational team first become aware of the event.

Initially reporting is achieved by completing an SAE report form and email to the Sponsor or their representative via the assigned project email address, which will be provided upon study setup.

If completion of an SAE form and emailing is not possible, reporting by telephone to Sponsor or their representative is required, and a completed SAE form must be emailed at the first opportunity.

Initial notification of an SAE by telephone to Sponsor must be confirmed in writing 24 hours from the time the site investigational team first becomes aware of the event using the SAE report form as described above.

As further information regarding the SAE becomes available, such follow-up information should be documented on a new SAE report form, marked as a follow-up report, scanned and emailed to the address at the bottom of the report form.

Withdrawal from the study in the event of an SAE and therapeutic measures taken shall be at the discretion of the Investigator. A full explanation for the discontinuation from the study should be made in the subject’s medical records and in the eCRF.

14.2.5. Clinical Laboratory Abnormalities and Other Abnormal Assessments as Adverse Events and Serious Adverse Events

Abnormal laboratory findings (e.g. biochemistry, hematology, and urinalysis) or other abnormal assessments (e.g. ECG and vital signs) per se are not reported as AEs. However, those abnormal findings that are deemed **clinically significant** by the Investigator and/or delegate or are associated with signs and/or symptoms must be recorded as AEs if they meet the definition of an AE (and recorded as an SAE if they meet the criteria of being serious) as previously described. Clinically significant abnormal laboratory or other abnormal findings that are detected after consent or that are present at Baseline and worsen after consent are included as AEs (and SAEs if serious).

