14.3.4. Laboratory Results

Table 14.3.4.1.1 Summary of Blood Tests- Stage 1 (Safety Population)

Table 14.3.4.1.2 Summary of Blood Tests- Stage 2 (Safety Population)

Table 14.3.4.2.1 Summary of Blood Tests Shifts from Baseline- Stage 1 (Safety Population)

Table 14.3.4.2.2 Summary of Blood Tests Shifts from Baseline- Stage 2 (Safety Population)

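### The laboratory tables in SAP 11.2 have no class above High, so no rule-based count by arm shows how far liver tests rise, although entry admits values up to 3.0 × ULN

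*SAP*

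**What the plan says.** SAP 11.2 (Safety Laboratory Assessments) states that results with a normal range "will be classified ('Low', 'Normal', 'High') in relation to the defined normal range limits", with a value equal to a limit counted as Normal. Two categorical displays for blood tests are built on those classes: the number of subjects out of range at each scheduled time point, and "shift tables that will represent the changes in normal range categories across post-baseline time points". The SAP table list (14.3.4) has one shift table per stage, for example "Summary of Blood Tests Shifts from Baseline- Stage 2 (Safety Population". Neither SAP 11.2 nor the table list uses multiples of ULN, CTCAE grades or a worst post-baseline value for laboratory results.

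The entry rule is wider than the normal range. Protocol 9.2, item 15, excludes subjects "with inadequate liver function at Screening defined as AST, ALT, ALKP, TBIL, or GGT" above a stated multiple, which the Synopsis gives as "gamma-glutamyl transferase (GGT) > 3.0 × upper limit of normal (ULN". Item 16 lets a subject with eGFR of 60 to below 90 enter if the Investigator considers the decrease not clinically significant or not due to dysfunction.

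The other laboratory outputs are continuous summaries of values and change from baseline at each scheduled visit (n, mean, SD, median, minimum, maximum; SAP 3.1 and 11.2) and by-subject listings. Protocol 14.2.5 says abnormal laboratory findings "per se are not reported as AEs". It then makes them AEs when they are judged clinically significant or come with signs or symptoms, and it expressly includes clinically significant findings already present at baseline that worsen.

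**The concern.** A shift table is meant to show how many subjects in each arm got worse and from what starting point. Here the scale stops at High, while the eligibility criteria allow subjects to be High on a liver test before the first dose. For such a subject a further rise changes neither the shift table nor the out-of-range count, because the subject is already counted. In subjects who start Normal, a trivial rise and a marked one are recorded identically.

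This matters because laboratory assessments belong to the Stage 1 primary endpoint and to the Stage 2 safety comparison with placebo (Protocol 7.2). In Stage 2 the AE route for a laboratory change runs through the Investigator's view of clinical significance, and the Investigator, site staff and Sponsor are all unblinded (Protocol 10.7). A table driven only by the measured value would not depend on that view, and the plan has none that grades the degree of abnormality.

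**Working it through.** The plan states no figure on this point, so there is nothing to reproduce. The check applies the SAP rule to example values.

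**Inputs**
- Class rule: below the lower limit is Low, above the upper limit is High, equal to a limit is Normal (SAP 11.2).
- Liver tests: excluded only above 3.0 × ULN at Screening (Protocol 9.2, item 15).
- eGFR: 60 to below 90 conditionally eligible (Protocol 9.2, item 16).
- Subjects: 50 CBL-514 and 25 placebo planned in Stage 2; 6 per Stage 1 dose group (Protocol 8.1).
- Assumed: the value pairs below, and an eGFR lower limit of 90 or 60. The documents do not give the laboratory's reference range.

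**Step 1: liver tests, in multiples of ULN.** The last column uses bands taken from the protocol's own limit: ≤ULN, >ULN to 3.0, >3.0.

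| Baseline to post-baseline | SAP table | Banded table |
|---|---|---|
| 0.9 to 1.1 | Normal to High | up one band |
| 0.9 to 8 | Normal to High | up two bands |
| 1.5 to 3.0 | High to High | same band |
| 2.5 to 5.5 | High to High | up one band |
| 3.0 to 10 | High to High | up one band |
| 3.0 to 25 | High to High | up one band |

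The SAP table gives one result for the first two rows and one for the last four. The liver result needs no assumption about the reference range, since any value above ULN is High and no higher class exists. The bands separate the first two rows and bring out three of the last four. They still do not split values above 3.0.

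**Step 2: eGFR.** With a lower limit of 90, falls from 75 to 55, 75 to 35 and 62 to 25 are all Low to Low. With a lower limit of 60, the same three falls are Normal to Low and do appear as shifts. The blind spot therefore depends on an unstated limit.

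**Step 3: the continuous summary.** Take one subject rising from 2.5 to 10 × ULN, with the others unchanged. The mean change moves by (10 − 2.5)/n:
- n = 50: 7.5/50 = 0.15 × ULN
- n = 25: 7.5/25 = 0.30 × ULN
- n = 6: 7.5/6 = 1.25 × ULN

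The maximum change at that visit would show 7.5 × ULN in each case. So an extreme case is visible in the maximum, and in a Stage 1 group also in the mean. The summary does not say how many subjects worsened or where they started.

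**Step 4: scheduled visits only.** SAP 3.1 and 11.2 restrict summary tables to scheduled visits, and SAP 3.1 keeps the original result when a test is repeated. A peak found at an unscheduled visit reaches the listings but not the tables.

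**The case against.** The strongest reply is that the information is available elsewhere. Protocol 14.2.5 makes clinically significant worsening from an abnormal baseline an AE, and it accepts that an abnormality without symptoms can be clinically significant. Such an AE is graded by CTCAE v5.0 (Protocol 14.2.1.1) and counted in the TEAE tables by SOC, PT and severity (SAP 11.1). The maximum change and the listings cover the rest. Protocol 16.2.2 asks only for listings and for summaries of observed values and change, so the SAP already does more than the protocol requires in a descriptive study.

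Most of this stands, and it rules out three stronger readings that a reader might infer.
- That worsening in subjects already out of range disappears from the report. It does not, for the reasons just given.
- That only changes with signs or symptoms can become AEs. Protocol 14.2.5 does not say that.
- That the gap weakens the pause criterion "for cardiovascular, renal or hepatic event considered to be at least possibly related to IP". That criterion (Protocol 8.4) acts on graded, related events during the study. The SAP tables are produced after database lock (SAP 14.2), and the Safety Review Committee reviews laboratory changes separately (Protocol 8.3).

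The objection does not answer one thing. The TEAE tables count only what the Investigator judged significant or linked to signs or symptoms, the maximum describes one subject per visit, and the listings give no comparison by arm.

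**Conclusion.** The point holds in a limited form. For AST, ALT, ALKP, TBIL and GGT, the planned categorical displays cannot register any rise in a subject who starts High, and they merge small and large rises from normal. For eGFR this is true only if the laboratory's lower limit is about 90. What the plan lacks is a rule-based count, by arm, of subjects whose values reach a worse level, independent of the unblinded Stage 2 Investigator's judgement.

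The size in subjects cannot be given, because the documents do not state how many are expected to be out of range at baseline. No endpoint, sample size or planned figure changes. This is a weakness of presentation in a descriptive safety analysis, and an inexpensive improvement worth making before the tables are produced.

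**What to change.** In SAP 11.2 and the table list in SAP section 17, add one shift table per stage from baseline to worst post-baseline value:
- AST, ALT, ALKP, TBIL and GGT, either by CTCAE v5.0 grade or by ≤ULN, >ULN to 3.0 × ULN, and >3.0 × ULN.
- eGFR by ≥90, 60 to <90, and <60, which removes the dependence on the laboratory's lower limit.
- Creatinine only if CTCAE grades are used, because 3.0 × ULN is not a protocol limit for it.

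Report the number of subjects moving to a worse category, by arm in Stage 2 and by dose group in Stage 1. State whether unscheduled results count towards the worst value. If CTCAE grades are chosen, write the cut-offs for each analyte into the SAP, since Protocol Table 9 gives only general severity descriptions. Keep Low/Normal/High for the other analytes.

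The cost is SAP wording and one more table per stage from data already collected, with some sparse cells. It is a reporting change only and leaves the stopping criteria and Safety Review Committee review as they are.
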